9.3. Variables

This is an observational study to access the real-world treatment practices and clinical outcomes in a Latin American population of adults' patients with acute leukemias. All treatment, procedures and overall management information of the target population will be collected according to the availability on the medical chart.

9.3.1. Outcomes

9.3.1.1. Primary Outcomes

- Description of demographic and clinical presentation characteristics at the moment of relapsed/refractory B-cell ALL or AML diagnosis.
- Treatment description considering the front-line therapy and subsequent regimen(s) required for patients with relapsed/refractory B-cell ALL and AML, including any systemic chemotherapy, target therapy, hematopoietic stem cell transplantation (autologous/allogenic), intrathecal chemotherapy and palliative management.

9.3.1.2. Secondary Outcomes

- Description of subtypes of AML and B-cell ALL based on the cytogenetic and molecular abnormalities, according to the WHO classification.
- Proportion of patients of each prognostic-risk group (favorable, intermediate, adverse) among newly diagnosed AML patients, based on cytogenetic profile
- Description of the treatment standard from diagnosis to inclusion of R/R ALL patients.
- Description of clinically relevant events presented by AML and relapsed/refractory B-cell ALL patients since treatment initiation until loss of follow-up or death from any cause.
- The EFS will be the measure of time since treatment initiation until failure to achieve complete remission (CR), or disease progression after CR, or death from any cause for both AML and relapsed/refractory B-cell ALL patients.
- The OS will be the measure of median time since treatment initiation until death from any cause for both AML and relapsed/refractory B-cell ALL patients.
- The OS will also assess the proportion of AML and relapsed/refractory B-cell ALL patients alive after 1, 3 and 5 years since treatment initiation.
- For AML patients who achieved CR, the RFS will be the measure of time since the CR attainment until relapse or death from any cause.
- For AML patients the response to induction and consolidation therapy will assess the proportion of patients who achieve complete remission (CR), complete remission with incomplete hematological recovery (CRI), complete remission without minimal residual disease (MDR-), partial remission (PR), and progressive disease.
- For relapsed/refractory B-cell ALL patients the response to the rescue treatment will assess the proportion of patients with complete remission (CR), complete remission without minimal residual disease (MRD-), partial remission (PR), and progressive disease.

- Heath care resource utilization description, considering the outpatient utilization, inpatient admissions, hospitalization length of stay, and concomitant medication prescription since diagnosis until the loss of follow-up or death from any cause.

9.3.2. Variables and Epidemiological Measurements

The information will be extracted only if available in the medical chart. No assumptions or interpretation should be done in order to describe the parameter of interest. The following variables will be collected:

- **Patient demographics:** age at diagnosis, gender at birth, country of residence.
- **Medical history:** comorbidities, family history, prior exposure to toxic agents, prior malignancy, therapy for prior malignancy, information on smoking, history of bleeding episodes.
- **Clinical information at diagnosis:** age at diagnosis, performance status (Karnofsky performance status [KPS] or Eastern Cooperative Oncologic Group [ECOG]).
- **Diagnosis information:** hematological parameters (total blood count, differential count, hemoglobin level), bone marrow aspirate/biopsy, cytogenetics, screening for gene mutations and rearrangements, immunophenotyping assessment.
- **Treatment information:** all treatment regimens used since diagnosis until loss of follow-up or death. It will include front-line induction therapies, consolidation therapies, rescue therapies, conditioning therapy, hematological stem cell transplantation (autologous/allogenic), intrathecal chemotherapy, palliative care.
- **Clinically relevant events:**
 - Hematological toxicities described as: febrile neutropenia, anemia/thrombocytopenia that requires blood transfusion, bleeding events.
 - Hematological stem cell transplantation (autologous/allogenic) and transplant complications such as graft-versus-host disease (GvHD), stem cell (graft) failure.
 - Gastrointestinal toxicities: oral mucositis, nausea, vomiting, diarrhea.
 - Hepatotoxicity: hepatic enzymes elevation, jaundice, ascites, abdominal pain.
 - Other events: tumor lysis syndrome, fatigue, dysgeusia, alopecia, muscle spasm, Infections and sepsis.
 - Secondary malignancy or central nervous system (CNS) involvement.
 - Any serious adverse even.t
- **Patient response at the end of treatment:**
 - Patient response according to International Working Group (IWG) criteria.⁶⁹
 - Methodology for the assessment of minimal residual disease.

PFIZER CONFIDENTIAL

- **Cytogenetic risk:**
 - Favorable, intermediate, adverse for AML.
 - Good, intermediate, poor, undetermined for B-cell ALL.
- **Healthcare resource utilization:** outpatient encounters (office visits, ancillary procedures, and ER visits), day-patient admission, inpatient admissions, hospitalization length of stay, concomitant medication (prophylactic therapy for infections, and other conditions related to the AML/ALL treatment or disease).

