7.2. Acute Lymphoblastic Leukemia

Unlike AML, acute lymphoblastic leukemia (ALL) affect mainly children and young adults. It is a disease with higher incidence in developing countries, with Honduras presenting the highest incidence rate in 2017 (3.83/100,000), followed by Mexico.⁵ The pathogenesis of ALL involves the abnormal proliferation and differentiation of a clonal population of lymphoid cells. In the majority of cases, it appears as a de novo malignancy in previously healthy individuals. Chromosomal aberrations are the hallmark of ALL, but are not sufficient to generate leukemia. Characteristic translocations include t(12;21)[ETV6-RUNX1], t(1;19)[TCF3-PBX1], t(9;22) [BCR-ABL1], rearrangement of MLL and a variant with a similar gene expression profile to (Philadelphia) Ph-positive ALL but without the BCR-ABL1 rearrangement.¹⁷

Most of the clinical manifestations of ALL reflect the accumulation of malignant, poorly differentiated lymphoid cells within the bone marrow, peripheral blood, and, extramedullary sites. In general, it is observed signs of bone marrow failure (anemia, thrombocytopenia, leukopenia) associated with general symptoms such as fever, weight loss, bleeding, fatigue, dyspnea and infection. Similarly, to the AML, the ALL can be also classified according to the WHO and FAB criteria.

The ALL can be originated from a progenitor cell of the B- or T-cell.¹⁸ The malignant cell expresses surface antigens according to their respective lineage developments and may influence the choice of the treatment. Therefore, precursor B-cell ALL cells (B-cell ALL) typically express on their surface membrane peptidase CD10, CD19, CD34, and nuclear terminal deoxynucleotide transferase (TdT), while precursor T-cell ALL cells are mainly CD2, CD3, CD7, CD34, and TdT.¹⁹

The genetic information of the leukemia cell can provide prognostic expectations and treatment directions.²⁰ About 20% of adults and a small percentage of children with ALL present *BCR-ABL* fusion gene, which characterizes the Philadelphia chromosome (Ph1).²¹ In contrast, the Ph1 occurs in only 1% to 2% of patients with AML. The identification of Ph1 by molecular analysis, such as reverse-transcriptase polymerase chain reaction (RT-PCR), is mostly important for B-cell disease.²² Besides Ph1, other chromosomal abnormalities are associated with poor prognosis and may also be investigated, such as *myc* gene rearrangements (in Burkitt leukemia), and *MLL* gene rearrangements.²³⁻²⁶

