 - Partial remission: a patient's response to treatment according to the medical chart. All hematologic criteria of CR; decrease of bone marrow blast percentage to 5% to 25%; and decrease of pretreatment bone marrow blast percentage by at least 50%.¹⁰
 - Progressive disease (PD): according to the medical chart. Progressive disease is usually accompanied by a decline in ANC and platelets and increased transfusion requirement and decline in performance status or increase in symptoms. Evidence for an increase in bone marrow blast percentage and/or increase of absolute blast counts in the blood is defined by European LeukemiaNet (ELN).¹⁰ as:

- >50% increase in marrow blasts over baseline (a minimum 15% point increase is required in cases with <30% blasts at baseline; or persistent marrow blast percentage of >70% over at least 3 months; without at least a 100% improvement in absolute neutrophil count (ANC) to an absolute level ($>0.5 \times 10^9/\text{L}$ [500/ μL], and/or platelet count to $>50 \times 10^9/\text{L}$ [50 000/ μL] nontransfused). According to ELN recommendations, the date of progression should then be defined as of the first observation date; or
 - >50% increase in peripheral blasts (white blood cell (WBC) \times % blasts) to $>25 \times 10^9/\text{L}$ ($>25 000/\mu\text{L}$) (in the absence of differentiation syndrome); or
 - New extramedullary disease.
 - Refractory disease: according to the medical chart. No CR or CRi after 2 courses of intensive induction treatment; excluding patients with death in aplasia or death due to indeterminate cause.¹⁰
 - Relapse from CR or CRi: according to the medical chart.^{40,53}
 - Appearance of leukemic blasts in the peripheral blood.
 - Appearance of extramedullary disease.
 - $\geq 5\%$ blasts in the bone marrow not attributable to another cause (eg, recovery of normal cells following chemotherapy-induced aplasia).
 - If there are no circulating blasts and no extramedullary disease and the bone marrow blast percentage is $\geq 5\%$
 - Tumor Lysis Syndrome (TLS): according to the medical chart. Descriptive TLS criteria are described in [ANNEX 3. ADDITIONAL INFORMATION: Appendix 2⁶⁸](#)

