8.3.2. Outcomes

Primary outcomes

1. Description of demographic and clinical presentation characteristics at the moment of R/R B-cell ALL or AML diagnosis
2. Treatment description considering the front-line therapy and subsequent regimen(s) required for patients with R/R B-cell ALL and AML, including any systemic chemotherapy, target therapy, hematopoietic stem cell transplantation (autologous/allogenic), intrathecal chemotherapy and palliative management.

Secondary outcomes

3. Description of subtypes of AML and B-cell ALL based on the cytogenetic and molecular abnormalities, according to the WHO classification

Effective Date: 01Feb2022

4. Proportion of patients of each prognostic-risk group (favorable, intermediate, adverse) among newly diagnosed AML patients, based on cytogenetic profile
5. Description of the treatment standard from diagnosis to inclusion of R/R ALL patients
6. Description of clinically relevant events presented by AML and R/R B-cell ALL patients since treatment initiation until loss of follow-up or death from any cause;
7. The EFS will be the measure of time since diagnosis until failure to achieve complete remission (CR), or disease progression after CR, or death from any cause for both AML and R/R B-cell ALL patients;
8. The OS will be the measure of median time since diagnosis until death from any cause for both AML and R/R B-cell ALL patients;
9. The OS will also assess the proportion of AML and R/R B-cell ALL patients alive after 1, 3 and 5 years, if feasible, since treatment initiation;
10. For AML patients who achieved CR, the RFS will be the measure of time since the CR attainment until relapse or death from any cause;
11. For AML patients the response to induction and consolidation therapy will assess the proportion of patients who achieve CR, complete remission with incomplete hematological recovery (CRI), complete remission without minimal residual disease (MDR-), partial remission (PR), and progressive disease
12. For R/R B-cell ALL patients the response to the rescue treatment will access the proportion of patients with CR, complete remission without MRD-, PR, and progressive disease
13. Health care resource utilization description, considering the outpatient utilization, inpatient admissions, hospitalization length of stay, and concomitant medication prescription since diagnosis until the loss of follow-up or death from any cause.

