 - B-lymphoblastic leukemia/lymphoma with t(12;21)(p13.2;q22.1); ETV6-RUNX1
 - B-lymphoblastic leukemia/lymphoma with hyperdiploidy
 - B-lymphoblastic leukemia/lymphoma with hypodiploidy
 - B-lymphoblastic leukemia/lymphoma with t(5;14)(q31.1;q32.3) IL3-IGH
 - B-lymphoblastic leukemia/lymphoma with t(1;19)(q23;p13.3);TCF3-PBX1
 - Provisional entity: B-lymphoblastic leukemia/lymphoma, BCR-ABL1-like
 - Provisional entity: B-lymphoblastic leukemia/lymphoma with iAMP21
- Immunophenotyping result

4. For each cytogenetic and/or molecular testing for newly AML, the risk stratification will be described with frequencies and absolute percentages for each treatment line:

newly AML and R/R AML

- AML cytogenetic risk classification according to 2017 European LeukemiaNet (ELN)
 - Favorable
 - Intermediate
 - Poor/Adverse

R/R B-cell ALL

- ALL cytogenetic risk classification
 - Good prognosis
 - Intermediate prognosis
 - Poor prognosis
 - Undetermined prognosis

5. Data from previous treatment lines from diagnose until study inclusion will be described for newly B-cell ALL patients and R/R B-cell ALL patients. For each treatment line, no statistical testing will be carried out. Only descriptive data will be reported (absolute number, frequency, mean ± standard deviation, median, interquartile range, minimum or maximum) for:

Newly B-cell ALL patients (treatment lines from ALL diagnose until study inclusion)

- ALL cytogenetic risk classification
- Regimen type.
- Drug regimen prescribed
- Treatment duration
- Time to next treatment
- Total number of cycles
- Number of patients with dose reduction;
- Number of patients with regimen withdraw;
 - Reasons of regimen withdraw;
- Radiotherapy
 - Duration, dose, and local of application
- Intrathecal chemotherapy
 - Drug administered intrathecally
- Stem cell transplant (SCT)

6. Clinically relevant events of newly AML and R/R B-cell ALL patients will be describe by treatment line and data will be reported as absolute number, frequency, mean ± standard deviation, median, interquartile range, minimum or maximum for:

newly AML

- Period of start of the event from start of first-line treatment;
- Clinical event description;
 - Hematological toxicities;
 - Gastrointestinal toxicities;
 - Hepatotoxicity.
- Most common adverse events description

R/R B-cell ALL

- Period of start of the event from start of first-line treatment;
- Clinical event description;
 - Hematological toxicities;
 - Gastrointestinal toxicities;

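### Hematological toxicities are counted from treatment start with no baseline, attribution or progression condition, so cytopenia or bleeding caused by the leukemia can be reported as toxicity and cannot be told apart from treatment effect

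*Protocol*

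**What the plan says.** Describing clinically relevant events is a secondary objective (Protocol 8.2, SAP 7.2). Protocol 9.3.2 lists the event classes, and the first reads "Hematological toxicities described as: febrile neutropenia, anemia/thrombocytopenia that requires blood transfusion, bleeding events". The entry has no grade, no comparison with the state before treatment and no causality condition.

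The counting window in Protocol 9.3.1.2 is "since treatment initiation until loss of follow-up or death from any cause". SAP 8.3.2 keeps it: "Description of clinically relevant events presented by AML and R/R B-cell ALL patients since treatment initiation until loss of follow-up or death from any cause". SAP 8.7.2 item 6 then sets the reporting: "Clinically relevant events of newly AML and R/R B-cell ALL patients will be describe by treatment line". It names hematological toxicities as an output for both cohorts and gives event onset relative to the start of first-line treatment. In the event list of SAP 8.7, secondary malignancy is the only entry tied to a drug cause.

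Two further provisions matter. Protocol 9.3.2 tells abstractors: "No assumptions or interpretation should be done in order to describe the parameter of interest". And some pre-treatment information is planned: blood counts at diagnosis, bleeding history, and laboratory results before and after each line (Protocol 9.3.2; SAP 8.7.2 items 1 and 2). None of it is linked to the event definition.

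**The concern.** The protocol itself attributes overlapping signs to the disease. Section 7.2 describes ALL as showing "signs of bone marrow failure (anemia, thrombocytopenia, leukopenia) associated with general symptoms such as fever, weight loss, bleeding, fatigue, dyspnea and infection". Every ALL patient qualifies through relapsed or refractory disease, so such signs may already be present when rescue treatment starts. Section 9.2.3 adds: "Progressive disease is usually accompanied by a decline in ANC and platelets and increased transfusion requirement". A non-responder transfused for that reason can appear as progressive disease in the response table and as a hematological toxicity in the event table.

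Reporting by line adds to the difficulty. Lines given for relapsed or refractory disease begin with active leukemia, and the plan sets no new baseline at the start of a line. The window also stays open after progression and through palliative care until death. A reader of a table headed toxicities will take the figures as harm from treatment, when an unknown part may be the leukemia.

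**Working it through.** **Step 1. The text, side by side.** Neither document gives a frequency for hematological toxicity, so there is no plan figure to reproduce.

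| Question | What the documents provide |
|---|---|
| Must the event be new or worse? | No such condition in Protocol 9.3.2 or SAP 8.7.2 item 6 |
| Must the chart attribute it to treatment? | Not for this class |
| Does counting stop at relapse or progression? | No; it runs to loss of follow-up or death |
| Can the abstractor separate the causes? | Not where the chart is silent, because interpretation is barred |
| Which signs overlap at presentation? | Anemia, thrombocytopenia and bleeding (Protocol 7.2, ALL only) |
| Which signs overlap at progression? | Falling platelets and neutrophils, more transfusion (Protocol 9.2.3) |

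**Step 2. Could another rule supply the missing condition?** The explicit-attribution rule in Protocol 11 and SAP 10 governs safety reports on the sponsor's products, not this outcome. Onset in SAP 8.7.2 item 6 is timed from the start of the first line. That can flag an event in the first days of that line, but it gives no baseline for a later line. The laboratory results around each line are described separately and do not feed the event count.

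**Step 3. How large could the effect be?** Two inputs are needed, and the documents give neither:

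- b = share of patients with the condition at line start (assumed 0.1 to 0.7)
- t = overall risk of a new or worsened event, independent of b (assumed 0.3 to 0.9)

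Assume also that every patient with the condition at line start is recorded as an event after it. Then:

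- reported share = b + (1 − b)t
- excess = b + (1 − b)t − t = b(1 − t)

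For b = 0.3 and t = 0.6, the reported share is 0.3 + 0.7 × 0.6 = 0.72. The excess is 0.72 − 0.60 = 0.12, which equals 0.3 × 0.4. To express this in patients, use the SAP 8.5 total of 200 + 300 + 100 + 100 = 700: 0.12 × 700 = 84.

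| b | t | Reported | Excess | Patients per 700 |
|---|---|---|---|---|
| 0.1 | 0.9 | 0.91 | 0.01 | 7 |
| 0.1 | 0.3 | 0.37 | 0.07 | 49 |
| 0.3 | 0.6 | 0.72 | 0.12 | 84 |
| 0.5 | 0.6 | 0.80 | 0.20 | 140 |
| 0.7 | 0.9 | 0.97 | 0.07 | 49 |
| 0.7 | 0.3 | 0.79 | 0.49 | 343 |

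The patient counts only give scale, because the planned tables split the 700 by disease and by line. Events caused by later progression are not modelled and would add to the excess.

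**The case against.** The strongest reply is that this is a labelling matter in one descriptive secondary outcome. Several parts of that reply stand.

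- **Reach of the overlap.** The list of presenting signs is in the ALL background only. The AML background has no such list, and AML is expected to be the larger group. The progression text does not name bleeding or anemia.
- **What abstractors are told.** The plan does not instruct anyone to code presenting cytopenia as toxicity. It permits that and offers no means of detecting it.
- **Unseen material.** The eCRF and the table workbook cited in SAP 13.1 are not in the public text and could hold a rule. None appears in SAP 8.7 or 8.7.2.
- **Limits of the data.** Bleeding history is taken at diagnosis. Bleeding or transfusion status before later lines is not among the listed items, and a test for worsening would need a threshold that neither document sets.

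Stronger readings are tempting but not supported. A reader might infer that the class mostly measures disease burden. That depends wholly on an assumed b, and the class also includes febrile neutropenia. A reader might infer that gentler regimens will look as toxic as intensive ones. No such comparison of events is planned: item 6 reports by line within each disease cohort, and the subgroups in SAP 8.7.6 apply to the primary objectives and to EFS, OS and RFS. Nor does the arithmetic settle it, since any effect on a contrast depends on how often already affected patients worsen, which the documents do not say. Finally, fatigue is also a presenting sign in Protocol 7.2, but both documents list it apart from the hematological class, so it needs no change here.

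The label and the open-ended count are not answered by any of this.

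**Conclusion.** The point holds in a limited form. As written, cytopenia or bleeding due to leukemia can be reported as hematological toxicity by treatment line, and the planned output cannot separate it from treatment effect. That it will happen often is not shown.

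The excess is b(1 − t). It runs from about 1 to 49 percentage points over the assumed ranges and is small where nearly every patient has a truly new event. The range rests on assumed values, on independence of b and t, and on every pre-existing condition being recorded after line start. It is not an estimate for this study. The primary objectives are unaffected.

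**What to change.** In Protocol 9.3.2 and SAP 8.7.2 item 6, rename the class 'Hematological events (any cause)', and let the event list in SAP 8.7 follow. Where the planned pre-line laboratory results, the counts at diagnosis or the chart document the state before the line, report in separate rows:

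- conditions already present at line start
- events after documented relapse or progression
- new events
- events in patients whose pre-line state is unknown

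Reserve the word toxicity for new events, or for events that the chart attributes to treatment.

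The cost is wording and a few extra table rows. No new data collection is needed. The unknown row may be sizeable for bleeding in later lines, but that shows the limit of the charts openly. The change concerns classification and reporting only.

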8.7. Data Analysis

Analyses will be descriptive in nature, as no hypothesis is being tested. Disease staging, comorbidities, demographic, clinical characteristics will be described at the date of diagnosis and/or treatment initiation for patients diagnosed with B-cell ALL R/R or AML. Treatment and clinical information will be assessed up to the most recent data available at the study enrollment. The treatments will be described in sequence according to the chronological order of administration. The duration through the number of cycles will be evaluated. Dose reduction information will also be collected. All analysis, including subgroup assessment, will be performed according to the data availability.

Continuous variables will be described as mean and standard deviation (SD), and/or as median, minimum, maximum, interquartile range (IQR, 25th and 75th percentiles). Categorical variables will be described by simple and cross contingency tabulation, with absolute frequencies and percentages. Missing values will be included in the denominators for the calculation of percentages and missing categories will be presented.

Follow-up period will be considered the time (in years) elapsed since B-cell ALL R/R or AML diagnosis until the study enrollment. It will be summarized as a continuous variable.

All time-to-event analysis will be described using Kaplan Meier methods and plots, if appropriate. The following definition and parameter analysis will be considered:

- Time to next treatment (TTNT) – considered as the time from the start date of the front-line therapy to the start date of a subsequent line of therapy. Patients without a subsequent line of therapy will be censored at study enrollment, last visit, last contact, or death, whichever comes first. It will be presented in months.
- Overall survival (OS) – considered as death from any cause from the time of initiation of diagnosis or treatment [12,13]. Patients not known to have died will be censored at study enrollment, last visit, last contact, whichever comes later. The median OS and, if feasible, the % of alive patients in 1, 3- and 5-years follow up of newly diagnosed AML and R/R B-cell ALL patients will be assessed.

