- Relapse-free survival (RFS) for newly diagnosed AML patients – considered as the date of achievement of a remission until the date of relapse or death from any cause; patients not known to have relapsed or died at last follow-up are censored on the date they were last examined, study enrollment, last contact, whichever comes later. Defined only for patients achieving CR, or CRI. The RFS will be measured as the treatment end date until next treatment initiation or date of death, whichever comes first, for all AML patients who achieved Complete remission/response (CR) or Complete remission/response with incomplete hematological/count recovery (CRI) at the end of treatment.
- Event-free survival (EFS) of newly diagnosed AML and R/R B-cell ALL patients – considered as the date of initiation of treatment (or date of diagnosis, if the previous is not available) to the date of primary refractory disease, or relapse from CR, or CRI, or death from any cause; patients not known to have any of these events are censored on the date they were last examined, study enrollment, last contact, whichever comes later. The EFS will be measured as the time since AML and R/R ALL initiation of treatment (or newly AML diagnosis and newly ALL diagnosis, if treatment date is not available) until i) treatment end date (or treatment start date of the next treatment line, if the previous is not available) when treatment response was Refractory disease(5) or Relapsed from CR or CRI or recurrent disease(6) as treatment response; ii) date of death, whichever comes first.
 - Clinically relevant events:
 - Hematological toxicities
 - Hepatotoxicity
 - Gastrointestinal toxicities
 - Tumor lysis syndrome
 - Fatigue
 - Dysgeusia
 - Alopecia
 - Muscle spasms
 - Infections

- Sepsis
- Secondary malignancy due to drug toxicity
- Death
- Other

Medical Dictionary for Regulatory Activities Terminology (MedDRA) version 2.1 (V2.1) or newer version will be used as a standardised medical terminology. Medicinal product names will be codified using World Health Organisation Drug Dictionary (WHODrug), a dictionary maintained and updated by Uppsala Monitoring Centre (UMC).

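### Abdominal pain is listed under hepatotoxicity with no qualifier or counting rule, so the reported hepatotoxicity percentage may include pain that is not hepatic

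*Protocol*

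**What the plan says.** Protocol section 9.3.1.2 makes clinically relevant events a secondary outcome: "Description of clinically relevant events presented by AML and relapsed/refractory B-cell ALL patients since treatment initiation until loss of follow-up or death from any cause". Section 9.3.2 names the events to collect. Two adjacent lines matter here:

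- "Gastrointestinal toxicities: oral mucositis, nausea, vomiting, diarrhea"
- "Hepatotoxicity: hepatic enzymes elevation, jaundice, ascites, abdominal pain"

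The same section limits how charts are read: "The information will be extracted only if available in the medical chart", and "No assumptions or interpretation should be done in order to describe the parameter of interest".

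SAP section 8.7 names 13 event categories. Hepatotoxicity is a bare heading among them, and the last category is Other. SAP section 8.7.2, item 6, sets the reporting: "Clinically relevant events of newly AML and R/R B-cell ALL patients will be describe by treatment line". For each disease cohort, item 6 names haematological, gastrointestinal and hepatic toxicity under the event description and adds a summary of the most common adverse events. On coding, SAP section 8.7 says: "Medical Dictionary for Regulatory Activities Terminology (MedDRA) version 2.1 (V2.1) or newer version will be used as a standardised medical terminology". Neither document links coded terms to the event classes.

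**The concern.** Abdominal pain is a non-specific symptom, and in patients on intensive chemotherapy it need not come from the liver. The protocol nevertheless places it under hepatotoxicity and not under gastrointestinal toxicity. It does not say whether one item is enough, whether items must occur together, or whether the chart must attribute the pain to the liver.

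The stake is what the hepatotoxicity percentage means. A patient with vomiting, diarrhoea and abdominal pain but normal liver tests could be counted in both classes. A reader of the tables could not tell how much of the hepatotoxicity figure reflects enzyme elevation, jaundice or ascites and how much reflects pain alone. If sites in the four countries read the list differently, the figure would also not be comparable between countries.

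**Working it through.** There is no figure in the plan to reproduce: neither document states a hepatotoxicity rate or an abdominal pain rate. The check has two parts.

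**1. How the list reads.** Four features of the protocol bear on whether one item is enough.

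- In the gastrointestinal line, each item plainly counts by itself; nausea alone is a gastrointestinal event. The hepatotoxicity line has the same form.
- Where section 9.3.2 wants a qualifier, it writes one. Anaemia and thrombocytopenia are tied to a need for transfusion. Abdominal pain carries no condition.
- Section 9.2.3 defers to the chart for many terms, tumour lysis syndrome among them. Hepatotoxicity has no entry there.
- Abstractors are told not to interpret, so they are not asked to sort hepatic from non-hepatic pain.

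These make the reading that any one item counts a natural one. They do not amount to a stated rule.

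**2. What that reading could do to the percentage.** Both inputs are assumptions.

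- h = share of patients with a true liver event.
- a = share of the remaining patients whose only listed item is non-hepatic abdominal pain.

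If any one item counts:

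reported share = h + (1 − h) × a, and excess = (1 − h) × a

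| h | a = 0% | a = 5% | a = 10% | a = 20% |
|---|---|---|---|---|
| 10% | 10.0% | 14.5% | 19.0% | 28.0% |
| 20% | 20.0% | 24.0% | 28.0% | 36.0% |
| 30% | 30.0% | 33.5% | 37.0% | 44.0% |

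For example, h = 10% and a = 20% gives 0.10 + 0.90 × 0.20 = 0.28, an excess of 18 points. At the other end, h = 30% and a = 5% gives 0.30 + 0.70 × 0.05 = 0.335, an excess of 3.5 points. For any a above zero, the relative distortion is greatest where true liver events are least common.

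The excess is zero if a = 0, or if sites record abdominal pain under hepatotoxicity only when the chart calls the event hepatic.

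**The case against.** The strongest reply is that section 9.3.2 is a list of variables to collect, not an endpoint algorithm. The four items can be read as manifestations to note once the chart documents hepatotoxicity. The instruction not to interpret supports that reading too, because turning charted abdominal pain with normal liver tests into liver toxicity is itself an interpretation. This stands. A reader might infer that the protocol scores abdominal pain alone as hepatotoxicity and that the percentage is therefore inflated. The documents do not support that, since no passage states a scoring rule and no rates are given.

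Several narrower replies also stand:

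- The SAP does not repeat the four-item list, and its Other category offers non-hepatic pain a place.
- The table shells are in an embedded spreadsheet that cannot be read here (SAP section 13.1), so components may already be shown separately.
- No total across classes is planned, so overlap between the two classes distorts no planned sum.
- SAP section 8.7 states "Analyses will be descriptive in nature, as no hypothesis is being tested", and no primary or survival outcome depends on this class.

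None of this removes the ambiguity. Nothing in the readable text of either document says that the chart must call the event hepatic, and the Other category does not take pain out of the hepatotoxicity total.

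**Conclusion.** The point holds as a classification gap with a possible upward bias. As written, the plan allows abdominal pain with no liver sign to enter the hepatotoxicity class and gives the reader no means of seeing it. Whether this happens, and how often, depends on how sites and programmers read the list. The range of 3.5 to 18 points rests entirely on the assumed values of h and a and on the reading that any one item counts; it illustrates scale and is not an estimate for this study. The reach is one category of one secondary descriptive outcome. It is a minor-to-moderate point, worth correcting because the change is small and makes the figure interpretable under either reading.

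**What to change.** Make two changes in SAP section 8.7.2, item 6, and align Protocol section 9.3.2 with them:

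1. State that abdominal pain alone does not qualify a patient for the hepatotoxicity class. Report it under gastrointestinal toxicities, or under Other, unless the chart also records enzyme elevation, jaundice or ascites, or attributes the pain to the liver.
2. Tabulate each hepatotoxicity component beneath the class total, by cohort and treatment line.

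If attribution or episode dates are not captured, use the component table with a class total that excludes isolated abdominal pain.

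The cost is a sentence in each document, a programming rule and a few table rows. It assumes that the eCRF stores the items separately, which the variable list suggests but does not prove. If they were captured as a single class, editing the text will not recover the split, and the report should say so. There is one small loss: hepatic pain charted with neither a liver sign nor an attribution leaves the class. If d is the share of patients with only such pain, the class total becomes h − d.
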